#### D. Estimates for incidence of vertical transmission of HIV infection.

In studies at Mulago Hospital, approximately 50% of antenatal women have been willing to receive their HIV results and nevirapine therapy.

Among children of mothers who do not receive anti-viral therapy, vertical transmission of HIV infection at 1 year is likely to be about 25%

Among children of mothers who receive nevirapine, vertical transmission at one year is reported to be about 12%, although it may be possible to reduce this further by avoiding breast-feeding, or by exclusive breast feeding for the first 3 months.

This gives an estimated overall incidence of vertical transmission of, at most, 18% at 1 year.

#### APPENDIX 3: The impact of helminths on the response to immunisation and on susceptibility to infectious diseases in childhood in Uganda. Proposed Study Profile.

First visit to the antenatal clinic.

• Women who live in study area; no history of adverse effects of anti-helminthics.

Т

- Consent to study of treatment in pregnancy.
- Screening investigations, including Hb, HIV, RPR, immunological studies.
- Provision of antimalarials and haematinics.
- Request stool sample.

	↓
On receipt of stool sample; gestation > 14	weeks; screening Hb results available.

 
Severe anaemia:
 
Treat with albendazole; exclude
 
Persistent diarrhoea with blood:
 
investigate and treat; exclude
 
	
 
Not severe anaemia:
 
Randomise to albendazole or placebo & praziquantel or placebo
 

At delivery.	

 
Mother:
 
Blood and stool samples
 
Nevirapine if known HIV+
 
	

Child:

Cord blood

Nevirapine if mother known HIV+

Post delivery.	↓
• Mass treatment with albendazole and praziquantel; selective treatment for Strongyloides .	• 1-2 samples post immunisation for studies of time course of immune response in selected participants.
	 ▼
	At one year.
	
 
Blood and stool samples
 
Specific treatment for worms found
 
Consent to study of treatment in childhood.
 
Randomisation to receive albendazole or placebo at 3 month intervals, starting at age 15 months
 

	Annual visits.
	Blood and stool

- Blood and stool
- Specific treatment for worms found

# APPENDIX 4: Plan for Analysis.

#### MOTHERS

At Antenatal Clinic Mothers will be investigated for helminth infections and randomised to receive albendazole (Alb+) or placebo (Alb-) and praziquantel (Pzq+)or placebo (Pzq-).															
Intestinal nematodes + Intestinal nematodes +						Inte	stinal n	ematod	les -	Intesti	nal nem	atodes -			
Schist	tosomia	nsis +		Schistosomiasis -			Schistosomiasis +				Schistosomiasis -				
Alb +		Alb		Alb +		Alb		Alb Alb			Alb +		Alb		
	D	-	D		D	-	D		D	-	D		ъ	-	D
Pzq	Pzq	Pzq	Pzq	Pzq	Pzq	Pzq	Pzq	Pzq	Pzq	Pzq	Pzq	Pzq	Pzq	Pzq	Pzq
+	-	+	-	+	-	+	-	+	-	+	-	+	-	+	-
G1	G2	G3	G4	G5	G6	G7	G8	G9	G10	G11	G12	G13	G14	G15	G16

At Delivery	
Helminths present, Treated	Helminths absent

#### **CHILDREN**

At One Year Follow-Up Children will be randomised to receive routine albendazole every 3 months or placebo, starting at 15 months. All will receive annual selective treatment based on stool examination.						
Group C1	Group C2					
Albendazole every 3 months and annual	Placebo every 3 months and annual					
selective treatment.	selective treatment.					

Annual Follow-Up Visits to Age 5 Years	
Helminths present, treated	Helminths absent

The analysis for the effect of maternal intestinal nematode infection will compare groups according to the presence or absence of intestinal nematodes at the antenatal visit, and whether or not they were treated; i.e. outcomes will be compared for children of mothers in groups G1-2-5-6 (intestinal nematodes, treated), G3-4-7-8 (intestinal nematodes, not treated), G9-10-13-14 (no intestinal nematodes, treated) G11-12-15-16 (no intestinal nematodes, not treated). The findings will be adjusted for the presence or absence of schistosomiasis, treatment with praziquantel, and the presence or absence of helminths at delivery. The overall effect of albendazole treatment during pregnancy will be determined by comparing G1-2-5-6-9-10-13-14 vs G3-4-7-8-11-12-15-16.

[figure not shown]
The analysis for the effect of maternal schistosomiasis will compare groups according to the presence or absence of schistosomiasis at the antenatal visit, and whether or not they were treated; i.e. outcomes will be compared for children of mothers in groups G1-3-9-11 (schistosomiasis, treated), G2-4-10-12 (schistosomiasis, not treated), G5-7-13-15 (no schistosomiasis, treated) G6-8-14-16 (no schistosomiasis, not treated). The findings will be adjusted for the presence or absence of intestinal nematodes, treatment with albendazole, and the presence or absence of helminths at delivery. The overall effect of praziquantel treatment during pregnancy will be determined by comparing G1-3-5-7-9-11-13-15 vs G2-4-6-8-10-12-14-16.

The analysis for the effect of intestinal nematodes in children will compare groups according to whether they receive routine albendazole every 3 months or annual selective treatment; i.e. outcomes for children in groups C1 and C2 will be compared. The presence or absence of helminths at annual follow up visits will be taken into account.

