#### Interventions and exposures.

Aims 1 & 2. To examine the effects of maternal infection with intestinal nematodes or schistosomiasis, and of the treatment of maternal nematode infection or schistosomiasis in **pregnancy.** Mothers will be randomised to receive albendazole or placebo and praziguantel or placebo during the second to third trimester of pregnancy. A marked reduction in IFN-y response after BCG immunisation has been demonstrated for children of mothers with schistosomiasis or filariasis but the effects of intestinal nematodes, and the effects of treatment of helminths in pregnancy, including both intestinal nematodes and Schistosoma sp, are not known. We will determine the effect of intestinal nematodes by comparing children of mothers with and without intestinal nematodes during pregnancy (Appendix 4). If intestinal nematodes have an effect similar to schistosomiasis or filariasis, treatment of all or any of these groups of helminths in pregnancy may be beneficial for the response to immunisation in the neonate. This will be determined for individuals known to have had helminths before treatment, and for all participants (Appendix 4). If, however, treatment leads to an increase in type 2 bias, as has been documented in studies for schistosomiasis (Appendix 1, Figure 3), suppression of the neonatal type 1 response may be increased. For the same reason, treatment in pregnancy may have benefits, or disadvantages, for the neonate's susceptibility to bacterial or viral infections. For vertical transmission of HIV infection, treatment in pregnancy may have benefits for the immune response, or may enhance vertical transmission through a transient rise in viral load (Appendix 1, Figure 1). Thus, for our objectives, a randomised trial of treatment in pregnancy is appropriate. Other considerations are as follows. Treating hookworm in pregnancy can reduce anaemia,  so women with hookworm and severe anaemia will be excluded from randomisation and treated. Treating helminths may improve the mother's general health, and hence birth outcome (stillbirths, perinatal deaths, birthweight), but this has not been demonstrated in controlled trials; and there is a possible risk of teratogenicity, but this may be confined to the first trimester. Therefore, although these outcomes are not the main issue for this study, they will be recorded and considered in an interim analysis.

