**Outcome (2): immunological responses to HIV in children of HIV-1 infected mothers.** Infants of HIV-infected mothers may be exposed to HIV in utero, at delivery or during breast-feeding. The neonatal immune response may have a role in determining vertical transmission. We will estimate the timing of HIV infection by DNA-PCR on blood spots from cord blood, and samples obtained at 6 weeks and 18 months after delivery. We will examine the effect of maternal helminth infections, and their treatment, on immune responses in cord blood and in infants at one year of age, by including HIV p24 antigen in the whole blood assay procedure. More detailed studies will be done on selected participants, using ELIspots or intracellular cytokine staining to identify responses by cell type and cytokine production. Cells will be stimulated with whole viral lysate, or with vaccinia constructs containing HIV genes to ensure class I presentation for CD8+ T cell responses. Potential confounding factors to be considered in these studies include possible associations between maternal helminth infection, or treatment of helminths, and maternal CD4+ T-cell count and viral load (Appendix 1), and the mother's choice of breast feeding practices. The numbers of subjects in the categories of maternal helminth infection and treatment will be small (Appendix 2 B), but will be sufficient to detect effects of a similar magnitude to those in our preliminary studies.

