#### Clinical

Malaria in pregnancy -film at enrolment - mother and placental film at delivery Malaria risk: environment, bednets, spraying Use of antimalarials in pregnancy Use of antihelminthics in pregnancy Haemoglobinopathies - may be possible to evaluate on stored samples

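### Appendix 4 adjusts the randomised treated-versus-untreated contrasts in helminth-infected mothers for helminths at delivery, which are a result of the treatment

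*Protocol*

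**What the plan says.** - **Randomisation.** Mothers are randomised when the antenatal stool is handed in, before it is read (Procedures, randomisation of mothers).
- **Aim.** Under Interventions and exposures, Aims 1 & 2, the effect of treatment is to be determined both in mothers infected before treatment and in all participants, with a pointer to Appendix 4.
- **Albendazole groups.** Appendix 4 compares G1-2-5-6 (infected, treated), G3-4-7-8 (infected, untreated) and the two matching uninfected groups, then states: "The findings will be adjusted for the presence or absence of schistosomiasis, treatment with praziquantel, and the presence or absence of helminths at delivery".
- **Praziquantel groups.** The parallel paragraph on schistosomiasis reads: "The findings will be adjusted for the presence or absence of intestinal nematodes, treatment with albendazole, and the presence or absence of helminths at delivery".
- **Overall effects.** Each paragraph ends with a separate sentence that compares all treated with all untreated mothers. Neither sentence names an adjustment.
- **Delivery stool.** The section on mothers at delivery says this sample serves to find infections that have persisted.
- **Children.** For the randomised comparison C1 versus C2, Appendix 4 adds: "The presence or absence of helminths at annual follow up visits will be taken into account".
- **HIV immune responses.** Outcome (2) lists possible associations of maternal infection or its treatment with maternal CD4 count and viral load as potential confounding. It does not say when these are measured.

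The protocol nowhere labels a model with delivery helminths as a mediation or direct-effect analysis.

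**The concern.** Infection status at enrolment is a pre-randomisation stratum, so treated versus untreated within it is protected by randomisation. Whether helminths are still present at delivery is decided in part by the drug. Putting that result in the model has two consequences. It takes out whatever part of the effect runs through clearance. It also compares unlike women: a treated mother who is still infected differs from an untreated mother who is still infected, for example in intensity or exposure, and such factors may also affect the child's outcome.

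At stake is the effect of treatment in infected mothers, for both maternal drugs. A reader of the report would take the adjusted figure for that effect, and it is not.

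**Working it through.** The protocol gives no figure for these contrasts. The timing settles the principle; the size can only be shown under assumptions.

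**1. Order of events.** Antenatal stool, then randomisation and drug, then delivery stool. Helminths at delivery are measured after randomisation and are affected by treatment. They cannot confound a randomised contrast.

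**2. Inputs.**
- From Appendix 2B (minimum expected numbers): nematodes 518 + 58 = 576 of 2500 mothers (23%); *S. mansoni* 270 + 30 = 300 (12%). With equal arms this is 288 and 150 per arm.
- From Ethical Considerations: a single stool may detect about 60% of infected mothers. The figure is for schistosomiasis; it is applied here to all helminths.
- From Sample size estimates: P<0.05, taken as two-sided.
- Assumed: total effect 0.25 SD in infected mothers; clearance 50-90% if treated and 10% if not. Appendix 1 brackets the treated range only loosely, in HIV-positive adults partly given other drugs: 15 of 30 still had helminths at the last visit, and 1 of 13 with *S. mansoni* only was still antigen-positive (12/13 = 92% clear).

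**3. Perfectly read stool, no shared cause.** Let Z be treatment, M helminths at delivery, c1 and c0 the clearance with and without treatment, and Y = dZ - bM + error. The total effect is d + b(c1 - c0). The model with Z alone returns this total. The model with Z and M returns d, which is (1 - mediated share) x total. Power is Φ(δ√(n/2) - 1.96); for n = 288, √(n/2) = 12.

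| Share through clearance | Adjusted effect (SD) | Power, 288 per arm | Power, 150 per arm |
|---|---|---|---|
| 0% | 0.25 | Φ(3.00 - 1.96) = 85% | 58% |
| 50% | 0.125 | Φ(1.50 - 1.96) = 32% | 19% |
| 75% | 0.0625 | Φ(0.75 - 1.96) = 11% | 8% |
| 100% | 0 | none | none |

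A simulation of 2,000,000 subjects at clearance 50%, 70% and 90% gave adjusted effects of 0.248 to 0.251, 0.121 to 0.126, 0.060 to 0.063 and -0.002 to 0.000 in the four rows.

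**4. Stool sensitivity 60%, full mediation.** Worked case with clearance 90% versus 10%, so b = 0.25/0.8 = 0.3125.
- Stool-negative mothers: truly infected 0.36/0.46 = 0.783 untreated and 0.04/0.94 = 0.043 treated. Difference in outcome: 0.3125 x 0.740 = 0.231.
- Stool-positive mothers: all infected, difference 0.
- Regression weights: 0.94 x 0.46/1.40 = 0.309 (negative) and 0.06 x 0.54/0.60 = 0.054 (positive).
- Adjusted effect: 0.231 x 0.309/0.363 = 0.197, a loss of 21%.

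Across clearance of 50-90%, with or without an assumed 20% of mothers carrying another species, simulation gave adjusted effects of 0.18 to 0.22 SD, losses of 13-27% and power of 59-74% at 288 per arm.

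**5. Shared cause.** Suppose an unmeasured factor raises persistence (probit coefficient 1) and lowers the outcome by 0.5 per SD. The unadjusted model still returns about 0.25. The adjusted estimate runs from 0.009 (clearance 50%, nothing mediated) to -0.555 (clearance 90%, all mediated).

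**6. Can the overall comparison stand in?** If the 0.25 SD effect is confined to infected mothers, the overall albendazole effect is 0.23 x 0.25 = 0.0575 SD. At 1250 per arm, √(1250/2) = 25, so power is Φ(1.44 - 1.96) = 30%. For praziquantel at 12%: 0.03 SD, Φ(0.75 - 1.96) = 11%. At 20%, the floor that Ethical Considerations gives for the pilot: 0.05 SD, Φ(1.25 - 1.96) = 24%.

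**The case against.** The strongest reply is that the main randomised comparisons are untouched. The overall albendazole and praziquantel effects are defined separately with no adjustment, and the cohort was sized on whole arms. The adjusted four-group models are introduced as analyses of maternal infection, which are partly observational. This stands, and it limits the scope. It does not remove the point: the same models contain the randomised contrast in infected mothers, Aims 1 & 2 name that effect as a target, and step 6 shows that the overall comparison may be a weak substitute.

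Several stronger readings are tempting, and the documents do not support them.
- *The adjustment removes much or all of the effect, or always pulls it toward zero.* No clearance rate or mediated share is given. Single-stool detection of about 60% weakens the adjustment. Ethical Considerations also describes antigen release boosting type 2 bias, a route that could oppose any benefit of clearance, so adjustment could enlarge or reverse the estimate.
- *C1 versus C2 is adjusted for a mediator.* The sentence names no method. It could mean stratification, or handling of the annual selective treatment that both groups receive.
- *Harm to HIV transmission would be adjusted away.* Aims 1 & 2 does say that treatment "may enhance vertical transmission through a transient rise in viral load", but the CD4 and viral-load remark belongs to children's immune responses to HIV. Transmission is under Outcome (3), where no such adjustment is set.
- *Placental malaria is another mediator in the models.* Appendix 7 lists "mother and placental film at delivery" among confounders or explanatory variables for maternal outcomes, without committing to adjust a randomised contrast.
- *Women who deliver elsewhere drop out.* How missing delivery stools are handled may be left to the SAP.

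Appendix 9 already lists maternal parasite burden and viral load among the delivery outcomes, so part of the sound approach is in place.

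**Conclusion.** The point holds for the treated-versus-untreated contrasts within infection strata, for both maternal drugs. As written, these are conditioned on a result of the treatment. The adjusted estimate is not the treatment effect and is not protected by randomisation.

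The documents do not determine the size. Under the assumptions above, the bias runs from none to complete loss, and with a shared cause the sign can reverse. The 0.25 SD effect, the clearance rates, the mediated shares, the 20% other-species rate and the strength of the shared cause are all assumptions. That the direction cannot be known in advance is itself a reason not to report the adjusted figure as a treatment effect.

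A reader might infer that the trial as a whole could report no effect because the analysis removed it. That does not follow, since the overall comparisons carry no stated adjustment. For C1 versus C2 and for Outcome (2), the text is open rather than wrong and needs clarifying.

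**What to change.** 1. In Appendix 4, remove helminths at delivery from both maternal adjustment lists wherever treated is compared with untreated. Keep enrolment infection status and the other randomised drug.
2. Label any model that includes delivery helminths as a secondary mediation or observational analysis.
3. State that C1 versus C2 is estimated without conditioning on helminths found at annual visits, and label any analysis that takes them into account as secondary.
4. In Outcome (2), limit any CD4 or viral-load adjustment of a randomised treatment contrast to pre-treatment values. The enrolment visit does not list a viral load, so if none is measured, leave viral load out of those contrasts.

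The cost is a change of wording in Appendix 4 and Outcome (2). No new data, visits or participants are needed.

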#### **Procedures**

#### Mothers: enrolment visit.

Women will be invited to participate in the study at their first antenatal visit if their normal residence is in the proposed study area (Entebbe Municipality; women from the additional, adjacent part of Katabi will be included later if necessary to maintain recruitment rates). Mothers who feel unable to decide to join the study at their first visit to the antenatal clinic, but who wish to do so at later visits, will be accepted provided that they accept all the study procedures, particularly the need for a blood draw on the day of screening.

They will be excluded if they have a history of adverse reactions to anti-helminthic drugs.

They will be excluded if, in the opinion of the doctor or midwife, the current pregnancy is not normal. Normal pregnancies would include twins. Abnormal pregnancies would include, for example, those in which the mother has gestational diabetes, pre-eclampsia or vaginal bleeding.

They will be excluded if they have already participated during an earlier pregnancy within the duration of the study. (Inclusion of more than one pregnancy and child for the same mother would complicate analysis, and the mother's behaviour with regard to antenatal care and use of antihelminthics for herself and her child might be influenced by earlier participation in the study.)

They will be asked to give informed consent for participation in the study of albendazole in pregnancy, and for follow up of the babies to one year of age.

A questionnaire regarding demographic and socio-economic details, clinical history and examination will be completed.

They will have blood drawn for full blood count, malaria slide, examination for microfilariae, HIV and syphilis serology and studies of the maternal immune response (30 ml).

Urine will be examined for protein and glucose using a dipstick.

They will be asked to provide a stool sample.

They will be provided with haematinics and antimalarial prophylaxis (an initial dose of Fansidar). Women with positive syphilis serology (RPR and TPHA) will be treated.

Tetanus immunisation will be given.

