#### Parasitology

• Stools will be examined by the Kato-Katz method for helminth ova, and by concentration for larvae.

- Serum will be examined for *Schistosoma* circulating anodic antigen (CAA) in HIV-infected women and their children, in whom stool examination is insensitive.
- Urine examination for *S. haematobium* will not be conducted as the prevalence is low in this area. None of 100 samples examined for S. haematobium in a previous study among HIV-positive adults was positive ([name], unpublished data).
- The prevalence of *Mansonella* infection has been found to be about 8% among HIV-positive adults in Entebbe using a modification of Knott's method. However, none of 50 samples tested for *Wuchereria bancrofti* antigen were positive (ICT Filariasis, Amrad ICT, Frenchs Forest NSW, Australia) ([name], unpublished data). The modified Knott's method will therefore be used to examine samples of maternal blood for *Mansonella*.
- Thick blood films and placental smears will be examined for malaria.
- External quality assurance for the Kato-Katz method will be contributed by the Vector Control Programme. The laboratory subscribes to the American College of Pathologists for quality assurance for general parasitology.

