**Outcome (3): the incidence of infectious diseases in childhood.** The effect of maternal and childhood helminth infection on disease incidence and severity will be examined in the whole cohort, with helminth species analysed separately and together. Pneumonia (Acute lower respiratory tract infection, ALRI) will be defined by World Health Organisation criteria, based on cough, respiratory rate and chest indrawing. Malaria will be defined as fever with a parasite density above a cut-off set using standard methods. Diarrhoea ( $\geq$ 3 loose stools per day, or the mother's definition) will be recorded as the principal disease event when there is no evidence of another cause. Measles will be diagnosed clinically using standard criteria and confirmed by measurement of specific antibody. Children with suspected tuberculosis will be investigated in detail, using gastric aspirates or material from other sites, as clinically indicated. Microscopy will be performed using fluorescence microscopy, and cultures using BACTEC as well as Lowenstein Jensen medium, for greater sensitivity. Proposed algorithms and new diagnostic tests, including the Ligase Chain Reaction (LCR), and whole blood culture with ESAT-6 will also be used and evaluated. HIV infection will be diagnosed by serology and polymerase chain reaction (PCR) in children aged 1-2 years.

Protocol amendment, January 2009. *TB infection* will be added as an outcome. T-spot.TB® assays will be performed for all five and six year olds. These investigations will allow us to determine the prevalence of T-spot.TB®-positivity at age five and six years and, hence, to estimate the prevalence of *TB infection* at age five, and the incidence of TB infection between age five and six years.

The immunological response to schistosomiasis in children exposed to schistosomiasis in utero. Protocol amendment, January 2009. There is increasing evidence that exposure to helminth

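### Appendix 4's analyses of maternal nematode and schistosome infection do not adjust for maternal Mansonella, although mothers are tested for it at enrolment

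*Protocol*

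**What the plan says.** - **Testing.** Protocol, Mothers: enrolment visit: "They will have blood drawn for full blood count, malaria slide, examination for microfilariae, HIV and syphilis serology". No subgroup restriction is given. Under Parasitology: "The modified Knott's method will therefore be used to examine samples of maternal blood for" *Mansonella*. The reason given there is that this "infection has been found to be about 8% among HIV-positive adults in Entebbe".
- **Why filariae matter to this trial.** Interventions and exposures, Aims 1 & 2: "A marked reduction in IFN-y response after BCG immunisation has been demonstrated for children of mothers with schistosomiasis or filariasis". The Background section cites the same evidence and adds maternal onchocerciasis.
- **Grouping.** Appendix 4 defines sixteen cells, G1 to G16, by four factors: intestinal nematodes, schistosomiasis, albendazole and praziquantel.
- **Adjustment.** For the nematode analysis: "The findings will be adjusted for the presence or absence of schistosomiasis, treatment with praziquantel, and the presence or absence of helminths at delivery". The schistosomiasis analysis adjusts for nematodes, albendazole and helminths at delivery.
- **Helminths at delivery.** Under Mothers: at delivery, persisting helminths are determined from the stool sample. The delivery blood is listed for a blood count, a malaria slide and immune studies, not for microfilariae.
- **Species analyses.** Outcome (3) promises that disease incidence will be examined "with helminth species analysed separately and together". Appendix 9 (pilot analysis d and main analysis b) mentions new helminth species and comparisons between species for the babies' responses. None of these places names *Mansonella*.

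**The concern.** The infected-versus-uninfected contrasts in Appendix 4 are observational, so they depend on the covariates in the model. The plan measures a third maternal helminth at baseline and gives a reason to think its class acts on a principal outcome, the infant response to BCG. It then leaves that infection out of both adjustment lists. The delivery covariate cannot stand in for it, because a stool examination is not the test the protocol uses for a blood filaria.

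If *Mansonella* and the stool helminths occur in the same women more often than chance, any effect of *Mansonella* on the child is partly attributed to nematodes or to *S. mansoni*. If they are independent, the omission adds some unexplained variation and no bias. In both cases, the stated models produce no *Mansonella* estimate to set beside the earlier work on maternal filariasis.

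**Working it through.** **Inputs from the protocol.** Appendix 2B gives a cohort of 2500 women (2250 HIV-negative, 250 HIV-positive) and minimum prevalences of 12% for *S. mansoni*, 23% for all nematodes and 32% for all worms. Parasitology gives *Mansonella* at about 8%, in HIV-positive adults only.

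**Reproducing the plan's own figures.** For all worms, 0.32 × 2250 = 720 and 0.32 × 250 = 80, as stated. For nematodes, 0.23 × 2250 = 517.5 and 0.23 × 250 = 57.5 (stated 518 and 58). For *S. mansoni*, 270 and 30, as stated. Combining the two infections under independence gives 1 − (1 − 0.12)(1 − 0.23) = 0.322, which matches the stated 32%. The source was stool examination by Kato-Katz only, so this figure does not count *Mansonella*.

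**Reference groups.**
- No nematodes: 2500 × 0.77 = 1925
- No schistosomiasis: 2500 × 0.88 = 2200
- Neither (G13 to G16): 2500 × 0.68 = 1700

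**Mothers with *Mansonella* in those groups.** Assumption: 8% applies to all mothers, independently of other worms. That gives 2500 × 0.08 = 200 in total.
- 1925 × 0.08 = 154 in the nematode-negative group
- 2200 × 0.08 = 176 in the schistosomiasis-negative group
- 1700 × 0.08 = 136 in G13 to G16, where *Mansonella* is the only one of these three infections

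For G13 to G16 the range is 68 at 4% prevalence to 340 at 20%. If only the 250 HIV-positive women carried it, the total would be 20.

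**Bias from leaving the term out.** On an additive scale, and ignoring the other covariates:

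bias = (p1 − p0) × filarial effect

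Here p1 and p0 are the *Mansonella* prevalences in mothers with and without the other infection. They are solved from q·p1 + (1 − q)·p0 = m and an assumed co-infection odds ratio (OR), where q is the prevalence of the other infection and m that of *Mansonella*. The protocol gives no co-infection odds ratio, so the values below are assumptions.

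| Contrast | m | OR 1 | OR 1.5 | OR 2 | OR 3 |
|---|---|---|---|---|---|
| Nematodes, q = 0.23 | 8% | 0 | 0.105 − 0.073 = 0.032 | 0.125 − 0.067 = 0.058 | 0.155 − 0.058 = 0.097 |
| Schistosomiasis, q = 0.12 | 8% | 0 | 0.110 − 0.076 = 0.034 | 0.135 − 0.072 = 0.063 | 0.177 − 0.067 = 0.110 |

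So about 3% to 10% of the filarial effect moves into the nematode estimate, and 3% to 11% into the schistosomiasis estimate. At 20% prevalence the corresponding range over both contrasts is 7% to 21%.

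**The case against.** **The labels are right.** Appendix 4 has no group called uninfected. Its reference groups are mothers without nematodes and mothers without schistosomiasis, and a mother with only *Mansonella* is placed correctly on both axes. The grouping also follows Aims 1 and 2, which concern those two infections. This stands: a reader might infer that infected mothers are misclassified, and they are not. What remains is an omitted covariate.

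**The evidence on *Mansonella* is indirect.** The protocol speaks of filariasis and onchocerciasis and does not show that *Mansonella* acts in the same way. The 8% comes from HIV-positive adults, while the cohort is expected to be 90% HIV-negative. This also stands, and it limits how large the problem can be said to be.

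**The plan leaves room elsewhere.** Outcome (3) and Appendix 9 foresee analyses by species, and a separate analysis plan could add the term. It is therefore too strong to say that *Mansonella* will go unanalysed. But those passages do not name it and do not alter the adjustment lists that Appendix 4 states.

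**Two larger figures are tempting.**
- *Power.* In a comparison of any helminth with none (800 versus 1700), moving 136 mothers to the infected side multiplies the effective sample size by (936 × 1564) / (0.92² × 800 × 1700) = 1.27. Power would rise from 80% to 88%, if *Mansonella* acted as strongly as the other worms. The arithmetic is sound, but Appendix 4 contains no such contrast, and Outcome (3) does not say that its combined analysis is limited to stool helminths.
- *False positives.* Suppose a filarial effect of 0.3 to 0.5 SD, an odds ratio of 2 to 3 and a standard error of √(1/575 + 1/1925) = 0.048 SD. A null nematode effect would then reach significance in 6.6% to 17.6% of trials. Neither the effect size nor the odds ratio has a source in the protocol, and the top value combines the most extreme choice of each.

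**Conclusion.** The concern holds as a gap in covariate adjustment. Appendix 4's two observational infection contrasts leave out a baseline infection that the protocol measures and whose class it cites as acting on the infant BCG response. The likely distortion is modest: about 3% to 10% of any filarial effect in the nematode contrast and about 3% to 11% in the schistosomiasis contrast. These ranges assume 8% prevalence in all mothers and a co-infection odds ratio of 1.5 to 3. The bias is zero if the infections are independent or if *Mansonella* has no effect on the outcome.

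A reader might infer that the trial's treatment results are at risk. They are not: the whole-arm albendazole and praziquantel comparisons are protected by randomisation. The case for changing the plan rests on the low cost of the adjustment and on obtaining an estimate for *Mansonella* itself.

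**What to change.** 1. In Appendix 4, add enrolment *Mansonella* (present or absent) to the adjustment terms of both the nematode and the schistosomiasis analysis, and report its estimate.
2. Wherever helminth species are analysed together, as under Outcome (3), define the helminth-free reference as negative on stool and on Knott's examination.

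The cost is one model term, one more estimate to report and a few words in Appendix 4. It needs no new samples and changes neither the randomisation nor the whole-arm comparisons.
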